### **13.4 Primary Objective, Endpoint(s), Analysis Plan**

A primary endpoint of the study is safety through the 6 month follow-up visit. Safety of the three escalating dose of WOKVAC will be assessed by adverse events as per CTCAE v4.0.

The type and grade of toxicities noted during the immunization regimen will be summarized. The duration of toxicities will also be summarized using descriptive statistics such as mean and standard deviation. All adverse events noted by the investigator will be tabulated according to the affected body system. The frequency and severity of adverse events will be summarized with a proportion and a 95% confidence interval. Despite lack of randomization, the incidence and severity of toxicity will be compared between successive dose groups using nonparametric test with the understanding that due to small sample size per dose group such test will have limited sensitivity to detect any small to moderate differences. These tests will be performed without adjustment for multiplicity of testing.

Demographic and baseline characteristics obtained at enrollment will be summarized in tabular or graphical formats with descriptive statistics.

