### **13.5 Secondary Objectives, Endpoints, Analysis Plans**

- To determine the immunogenicity of WOKVAC Th polyepitope plasmid based vaccine in patients with breast cancer at 3 escalating doses.
- To evaluate for the presence of a Th2 immune response by antibodies against the WOKVAC antigens
- To determine whether a WOKVAC Th polyepitope plasmid based vaccine elicits a persistent memory T cell response.
- To evaluate whether WOKVAC vaccination modulates T regulatory cells (Treg) and myeloid derived suppressor cells (MDSC).
- To determine a recommended phase 2 dose for further breast cancer prevention studies.
- To assess the long-term effects of 3 escalating doses of a deoxyribonucleic acid (DNA) plasmid

based vaccine encoding three breast cancer antigens (IGFBP-2, HER2, and IGF-1R) in patients with breast cancer, for 5 years from enrollment to satisfy the evaluation requirements for the Food and Drug Administration (FDA)

Immune responses as measured by IFN-g ELISPOT will be summarized with mean and standard deviation or median and range over time, the change over time will be summarized with graphs, and also analyzed using linear mixed-effects regression models with normalizing transformation if necessary. Each patient would be given a value at each immune evaluation that is the sum of the median response to HER2, IGFBP-2 or IGF1R, and a composite median would be calculated for each WOKVAC dose level.

Antibody immunity will be assessed as an additional measure of a Th2 response. A humoral immune response will be measured by ELISA and serum antibody avidity for IGFBP-2, HER2, and IGF-1R (using ELISA) to determine an avidity index (AI) before and after vaccination. Low avidity antibodies will have an AI <30%, moderate avidity antibodies 30-50% and high-avidity antibodies 51-100%. Patients will be considered to have developed an antibody response if antigen specific IgG antibodies are both detectable and have moderate to high avidity.

Memory T cell response will be summarized with proportion over time, and the change over time will be summarized with bar charts, and analyzed using generalized linear mixed effects regression models with suitable link function.

Treg cell, and MDSC levels will be summarized with mean and standard deviation or median and range over time, the change over time will be summarized with graphs, and analyzed again using linear mixed-effects regression models with normalizing transformation if necessary.

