Analyses of the above secondary endpoints will be descriptive in nature by necessity. Despite lack of randomization, we will compare the immunologic efficacy between the 3 dose levels data using linear dose-response relationship with a regression analysis. Normalizing transformation will be used as well if necessary. The linear regression model will have a 0.80 power to detect an anticipated effect size (defined as  $R_2/(1-R_2)$ ) of 0.281 according to the level 0.05 F-test, given the sample size of 30.

Once the dose escalation is completed, key study personnel in concert with the NCI/DCP staff will review the toxicity, immunogenicity, antibody immune response, memory T cell response, Treg, and MDSC, and make a recommendation for a phase 2 dose. Statistical tests will only be advisory due to lack of randomization and limited sensitivity of such tests given the small sample size for each dose group. We may seek other experts in this deliberation.

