### **13.9 Evaluation of Response**

The number of patients traditionally required to gather preliminary data on the safety of a dose in a phase I study is less than the number needed to evaluate immunologic responses and differences in the immunologic responses between cohorts of patients. Since Phase I tumor vaccine studies to date have proven to be relatively free of serious toxicity, the defining endpoint that would move a study forward to a more extensive phase II efficacy trial will likely be immunogenicity. In order to have meaningful immunologic data, the study will accrue 30 evaluable patients (10 patients per dose arm). When accrual is complete, we will: (1) determine if the WOKVAC vaccine elicits specific cellular and humoral immune responses for each antigen, and persistent antigen specific memory T cells can be detected and (2) which dose is most immunogenic. We expect that there may be differences in immune response between dose-levels. Moreover, the dose-level that is determined to be the most biologically relevant in terms of stimulating immunity may not be the highest dose.

Immune responses will be evaluated for patients who complete the vaccination series with both a baseline and a one month post vaccination series blood draw. Durability of generated immune responses will be evaluated in patients who complete the vaccination series with both a baseline and a 6 month post vaccination series blood draw.

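### Section 13.5 compares immune response between doses only through one linear dose term and states no interval or contrast for 300 versus 600 mcg, so a peak at 300 mcg could not be told from chance.

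*Combined protocol and SAP*

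**What the plan says.** Section 13.9 says that, once accrual is complete, the trial will determine "which dose is most immunogenic". It adds that "the dose-level that is determined to be the most biologically relevant in terms of stimulating immunity may not be the highest dose". It also expects immunogenicity, more than toxicity, to decide whether the vaccine moves to phase 2.

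For immune response, Section 13.5 states:

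- a descriptive summary: "Immune responses as measured by IFN-g ELISPOT will be summarized with mean and standard deviation or median and range over time";
- a per-dose figure: "a composite median would be calculated for each WOKVAC dose level";
- mixed models, described for change over time, with no dose term or dose contrast mentioned;
- one between-dose comparison: "we will compare the immunologic efficacy between the 3 dose levels data using linear dose-response relationship with a regression analysis".

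The sample-size statement belongs to that comparison: "The linear regression model will have a 0.80 power to detect an anticipated effect size" of 0.281, on the R²/(1−R²) scale, at level 0.05 with 30 patients. The same section limits the weight of testing: "Statistical tests will only be advisory due to lack of randomization" and because of the small dose groups.

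Section 13.4 treats toxicity differently. There "The frequency and severity of adverse events will be summarized with a proportion and a 95% confidence interval", and successive dose groups are compared with a nonparametric test. Section 13.5 states no counterpart to either for immune response.

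**The concern.** A line in dose rises, falls or stays flat. A monotone normalizing transformation of the response does not change this. The one stated between-dose test therefore cannot show a best dose in the middle, which Section 13.9 treats as possible.

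The composite medians can show it, but medians always name a highest dose, even when the three doses are equal. If 300 mcg comes out on top, the phase 2 dose review faces three readings: a real fall at 600 mcg, a plateau from 300 mcg, or chance. The plan states no measure of precision to help separate them, and the linear test does not do so. What is at stake is the choice between 300 and 600 mcg. A steady trend, or a drop only at 600 mcg, is within the line's reach.

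**Working it through.** **Inputs.** Effect size f² = 0.281, level 0.05, N = 30, power 0.80 (Section 13.5); 10 evaluable patients per arm (Section 13.9), at most 12 (Section 13.3); doses 150, 300 and 600 mcg. Assumed, because the documents give no means or SD: normal data, within-dose SD 1, and the mean patterns below.

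**1. The plan's figure.** With noncentrality 0.281 × 30 = 8.43, the F-test has power 0.800 on (1, 28) df and 0.690 on (2, 27) df. The stated 0.80 reproduces, and it fits a single slope. A three-level dose factor would need f² = 0.360 for 0.80.

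**2. Mean patterns at the plan's effect size.** With SD 1, f² is the variance of the three means.

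- Peak (0, d, 0): d²/3 − (d/3)² = (2/9)d² = 0.281, so d = 1.124. The plateau (0, d, d) and the drop at 600 mcg only (0, 0, −d) have the same variance and the same d.
- Half-fall (0, d, d/2): variance d²/6 = 0.281, so d = 1.298.

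**3. What a line can capture.** The dose deviations from their mean of 350 mcg are −200, −50 and 250, with sum of squares 105,000. For the peak, the slope's sum of squares per patient is (50d)²/105,000 = 0.0238d². The between-dose total is (2/3)d², so the share captured is 3.6%. On log dose the deviations are −1, 0 and 1, and the share is zero. For the drop at 600 mcg only, it is (250²/105,000)/(2/3) = 89% on the mcg scale.

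**4. Simulation,** 100,000 to 200,000 trials per pattern, 10 per arm:

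| True means at 150, 300, 600 mcg (SD) | Linear test significant, mcg (log dose) | 300 mcg has top median | 95% interval for 600 − 300 wholly below zero |
|---|---|---|---|
| Peak: 0, 1.12, 0 | 5% (3%) | 97% | 68% |
| Half-fall: 0, 1.30, 0.65 | 10% (22%) | 89% | 29% |
| Plateau: 0, 1.12, 1.12 | 52% (66%) | 50% | 2.5% |
| No dose effect: 0, 0, 0 | 5% by design | 33% | 2.5% |

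For the drop at 600 mcg only, the linear test is significant in 74% (65% on log dose).

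In the half-fall, nearly all significant slopes are positive, so they point towards 600 mcg although 300 mcg is best. A significant positive slope occurs in 10% of trials (22% on log dose). For the peak it occurs in 0.3% (1.4%).

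Among trials where 300 mcg has the top median, it exceeds the 600 mcg median by 0.47 SD on average with no dose effect, and by 0.42 SD under the plateau. With no dose effect, the gap is at least 0.5 SD in 41% of those trials.

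**5. Precision of a stated contrast.** With the SD pooled over three arms of n, the half-width is t(0.975, 3n − 3) × √(2/n).

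- n = 8: 2.080 × 0.500 = 1.04 SD
- n = 10: 2.052 × 0.447 = 0.92 SD
- n = 12: 2.035 × 0.408 = 0.83 SD

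At n = 10, a pairwise difference needs about 1.30 SD for 80% power.

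**The case against.** The case on the other side has four parts.

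- **Advisory status.** The plan calls these analyses descriptive and the tests advisory. The phase 2 dose comes from a joint review of toxicity, immunogenicity, antibody, memory T cell, Treg and MDSC data, and no rule ties the dose to the slope. This stands, and it limits the weight of the point.
- **Other yardsticks exist.** Sections 9.1.1 and 13.6 define successful immunization for each antigen (IFN-g precursor frequency above 1:20,000, or more than twice baseline where immunity pre-exists), and this could be tabulated by dose. If means and SDs were reported by dose, a reader could also work out the interval by hand. Both are true. But a responder rate with no interval has the same gap as the medians, and the plan does not say that the mean and SD summaries are by dose.
- **The remedy is only partly decisive.** The interval excludes zero in 68% of peak trials but only 29% of half-fall trials. Both proposed intervals together indicate a peak in about 54% and 28%. The 2.5% false indication rate is unconditional. Among trials where 300 mcg already has the top median, it is about 6% with no dose effect and 5% under the plateau. These limits are real. Even so, a wide interval is informative here, because it warns against over-reading a gap of 0.4 to 0.5 SD.
- **The peak is an assumed shape.** The plan defines 0.281 for the linear model and gives no particular reason to expect a sharp peak at 300 mcg. Section 13.9 also fits a decline at the top dose, which the line detects reasonably well, or a plateau. This narrows the gap to the 300-versus-600 mcg choice but does not close it.

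**Conclusion.** The concern holds, as an optional improvement. The only stated between-dose test of immune response cannot show a peak at 300 mcg, and nothing stated in Section 13.5 measures the precision of a 300-versus-600 mcg difference. At the plan's own effect size, a true peak would usually be visible in the medians (97%) but almost never in the linear test (5%, or 3% on log dose). A top median at 300 mcg would also appear in a third of trials with no dose effect and in half of trials with a plateau. There is no power error: 0.80 is right for a straight-line response. The rates rest on normal data, equal SDs, 10 per arm and the assumed mean patterns; that a line cannot peak in the middle rests on none of these. The gap does not by itself decide the phase 2 dose.

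**What to change.** Keep the linear trend test and its 0.80 power, and add that this power applies to a straight-line response only. For the same immune outcome, on the transformed scale if one is used:

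- fit a model with dose as a three-level factor;
- report the 300-minus-150 and 600-minus-300 mcg differences with 95% confidence intervals, marked as unadjusted and advisory;
- state the expected half-width of about 0.92 SD at 10 per arm;
- list the two differences beside the composite medians as inputs to the phase 2 dose review, with a note that an interval read because 300 mcg came out on top is somewhat less protective than its nominal level.

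If the 2-df F-test is also reported, give its power at N = 30: 69% at effect size 0.281 and 80% at 0.360.

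The cost is a few sentences and a little more analysis, with no change to patients, doses, samples or assays. The drawbacks are wide intervals and two more unadjusted comparisons, which Section 13.4 already accepts for toxicity.

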### 13.6 Outcome measures

1. Primary endpoints: Safety through 6 month follow-up visit will be assessed per CTEP CTCAE v. 4.0.
2. Secondary endpoints:
  - a. Immunogenicity will be evaluated via an assessment of the generation of IGFBP-2, HER2, and IGF-1R specific IFN-g and IL-10, IFN-g/IL-10 ratios, inducing T cells, Th1:Th2 ratios and IgG antibodies.
    - (i) Cellular immune response will be defined by the magnitude of the Th1 (IFN-gamma (g)) antigen specific immune response using ELISPOT. Successful immunization will be defined by generating a protein specific IFN-g precursor frequency greater than 1:20,000 PBMC for each antigen. In patients with pre-existent immunity, responses must augment over 2 times baseline for immunization to be considered successful.
    - (ii) Humoral immune response will be measured by ELISA and serum antibody avidity for IGFBP-2, HER2, and IGF-1R to determine an avidity index (AI) before and after vaccination. Low avidity antibodies will have an AI <30%, moderate avidity antibodies 30-50% and high-avidity

antibodies 51-100%. Patients will be considered to have developed an IGFBP-2 antibody response if antigen specific IgG antibodies are both detectable and have moderate avidity.

- b. To detect persistent T cell memory, flow cytometry panels will be used to evaluate antigen specific central and effective memory phenotypes prior to and at 1 and 6, months after immunizations have ended for all 3 doses.
- c. To detect modulation of Tregs and MDSC with vaccination, levels over the course of immunization will be assessed by flow cytometry of PBMC.
- d. Long-term safety including vaccine toxicity and overall relevant health status.

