### 8.2 Secondary Endpoints

Secondary endpoints of the study include the immunogenicity of WOKVAC Th polyepitope plasmid based vaccine, antibody response to the three WOKVAC targets, memory T cell response, modulation of (Treg), and MDSC in patients with breast cancer at three escalating doses.

These secondary endpoints will be used to determine whether an immune response is observed between the three doses and to determine a recommended phase 2 dose for further cancer prevention studies as detailed in Section 13.5. Determining a phase 2 dose will be performed by key study personnel and NCI/DCP staff. The recommendation will be based on dose level safety/tolerance, immunogenicity, memory T cell response, T cell response, Treg and MDSC data.

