## 9. CORRELATIVE/SPECIAL STUDIES

### 9.1 Rationale for Methodology Selection

#### 9.1.1. Immunogenicity of the 3 doses will be evaluated by an assessment of the generation of IGFBP-2,

HER2, and IGF-1R specific T cells (both Th1 and Th2).

Cellular immune response will be defined by the magnitude of the Th1 (IFN-gamma (g)) vs. Th2 (IL-10) antigen specific immune response using ELISPOT. Successful immunization will be defined by generating a protein specific IFN-g precursor frequency greater than 1:20,000 PBMC for each antigen. In patients with pre-existent immunity, responses must augment over 2 times baseline for immunization to be considered successful.

Exploratory analysis will assess whether patients maintain a Th1 dominant immune response to all three antigens over time.

Antibody immunity will be assessed as an additional measure of a Th2 response.

A humoral immune response will be measured by ELISA and serum antibody avidity for IGFBP-2, HER2, and IGF-1R (using ELISA) to determine an avidity index (AI) before and after vaccination. Low avidity antibodies will have an AI <30%, moderate avidity antibodies 30-50% and high-avidity antibodies 51-100%. Patients will be considered to have developed an antibody response if antigen specific IgG antibodies are both detectable and have moderate to high avidity.

- 9.1.2. To detect persistent T cell memory, flow cytometry panels will be used to evaluate antigen specific central and effector memory phenotypes prior to vaccination and at 1 and 6 months after immunizations.
- 9.1.3. To detect modulation of Tregs and MDSC with vaccination, levels over the course of immunization will be assessed by flow cytometry of PBMC.

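### Section 13.6 counts only moderate-avidity antibody, and names only IGFBP-2, where 9.1.1 and 13.5 count moderate to high avidity for any vaccine antigen

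*Combined protocol and SAP*

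**What the plan says.** Sections 9.1.1, 13.5 and 13.6(ii) describe the same humoral assay: ELISA for IgG plus an AI, with identical classes (low below 30%, moderate 30-50%, high 51-100%). Each then gives a responder rule.

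- Section 9.1.1 counts a response "if antigen specific IgG antibodies are both detectable and have moderate to high avidity".
- Section 13.5: "Patients will be considered to have developed an antibody response if antigen specific IgG antibodies are both detectable and have moderate to high avidity".
- Section 13.6(ii): "Patients will be considered to have developed an IGFBP-2 antibody response if antigen specific IgG antibodies are both detectable and have moderate avidity".

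On antigens, 8.2 lists as a secondary endpoint the "antibody response to the three WOKVAC targets". Section 13.9 says that at the end of accrual the study will "determine if the WOKVAC vaccine elicits specific cellular and humoral immune responses for each antigen". The item in 13.6 that names only IGFBP-2 also measures "serum antibody avidity for IGFBP-2, HER2, and IGF-1R to determine an avidity index (AI) before and after vaccination".

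On baseline status, the only explicit rule belongs to the cellular endpoint, in 9.1.1 and 13.6(i): "In patients with pre-existent immunity, responses must augment over 2 times baseline for immunization to be considered successful". No section has a matching sentence for antibody.

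On use, the last paragraph of 13.5 names antibody response among the data reviewed for the phase 2 dose recommendation.

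**The concern.** An analyst who takes the endpoint from 13.6, whose title is outcome measures, would classify patients differently from one who takes it from 13.5. The two rules disagree on the highest-avidity antibodies: 13.5 calls them a response and 13.6 does not. Section 13.6 also stops at IGFBP-2, so it gives no rule for two of the three antigens that the same item measures. Nothing in the plan says which section governs.

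The stake is a descriptive proportion per antigen and arm. It is one of the items in the dose review, and 2.3.3 also looks to antibody development to support the view that the vaccine is mainly Th1. Both uses need a single definition.

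**Working it through.** **Reproducing the plan's figure.** The only stated power figure is 0.80 for a linear dose-response regression (13.5: effect size 0.281, n = 30, level 0.05 F-test). With one predictor, the degrees of freedom are 1 and 28 and the noncentrality is 0.281 × 30 = 8.43, which gives power 0.8003. The figure reproduces and does not depend on the antibody rule.

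**Setting the rules side by side** for a patient with detectable IgG:

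| AI | 9.1.1 and 13.5 | 13.6(ii) as written |
|---|---|---|
| below 30% | no response | no response |
| 30-50% | response | response |
| 51-100% | response | no response |

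For antigens, 9.1.1 and 13.5 carry no limit, while 13.6(ii) states its rule for IGFBP-2 only.

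**Size per patient.** Take 10 evaluable patients per arm (13.9). For one antigen, let r be the number with detectable IgG and AI of at least 30%, and h the number of those with AI 51-100%.

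- Rate under 9.1.1 and 13.5 = r/10.
- Rate under literal 13.6 = (r − h)/10.
- Gap = h/10, or 10 percentage points for each such patient.

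The documents give neither r nor h. As an assumed illustration with r = 6, the 13.5 rate is 60%. For h = 0, 2, 4 and 6 the 13.6 rate is 60%, 40%, 20% and 0%. If no patient exceeds 50%, the rules agree for IGFBP-2.

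**Baseline.** The rule describes status, but a patient is said to have *developed* a response and AI is measured before and after vaccination, so a change from baseline is implied. Section 2.3 reports that breast cancer patients can have humoral as well as cellular immunity to these proteins, so some may meet the criterion before vaccination. Let b be the number per arm who do and do not change. A status-only reading counts them and a change reading does not. With all 10 in the denominator, the difference is 10b points. The documents give no value for b; an assumed range of 0 to 4 gives 0 to 40 points.

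**Sample used.** Section 13.9 evaluates immune response in patients who complete the series and have baseline and one-month samples, and durability in completers with baseline and six-month samples. Section 5.7.2 accepts baseline plus any one post-vaccine research sample. Research blood after vaccination is drawn at one and six months (10.2), so a patient with only the six-month sample is evaluable under 5.7.2 but not for the one-month response in 13.9.

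**The case against.** The strongest reply is that 13.6 contains a slip that nobody would apply. Two of three statements agree, one of them is in the analysis-plan section, and a rule that treats the best-binding antibodies as non-response makes no immunological sense. The endpoint is secondary and descriptive, 13.5 attaches no model or test specifically to antibody responder rates, and statistical tests are only advisory in the dose decision. All of this limits the weight of the point. It does not remove the mismatch, because the sentence sits in the outcome definitions and no order of precedence is given.

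A reader might also infer more than the documents support:

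- *That 13.6 drops HER2 and IGF-1R.* It does not exclude them. The same item measures all three, and the 13.5 rule covers any vaccine antigen. Section 13.6 is incomplete here rather than opposed to 8.2 and 13.9.
- *That 8.2 makes antibody a dose criterion through the word immunogenicity.* The bases in 8.2 are "dose level safety/tolerance, immunogenicity, memory T cell response, T cell response, Treg and MDSC data". Section 13.6 groups IgG under immunogenicity, but 8.2's own endpoint list and the dose-review list in 13.5 both name antibody separately. Only 13.5 clearly makes it an input.
- *That the dose order could reverse, because a dose that raises avidity above 50% lowers its own rate.* Numbers can be chosen to show this, but every input would be assumed and the literal 13.6 reading would have to be applied. Antibody is also described as an additional Th2 measure, not a rate to be maximised.
- *That scoring of baseline-positive patients is wholly open.* The wording already points to excluding unchanged antibody. What is unsettled is how to treat a rise in someone already positive.

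**Conclusion.** The inconsistency is real and should be corrected. Under the plan's own classes, 13.6 as written scores AI 51-100% as non-response where 9.1.1 and 13.5 score it as response, and 13.6 has no responder rule for HER2 or IGF-1R. The effect is 10 percentage points per affected patient, antigen and arm, assuming 10 evaluable patients per arm. The number affected cannot be derived from the documents. The cause is probably a drafting slip. Primary safety, the sample size and the 0.80 power statement are untouched. The point matters because antibody response is one of several inputs to the phase 2 dose review in 13.5. Stating the baseline rule and the sample is a useful clarification, but the conclusion does not depend on it.

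**What to change.** Replace the responder sentence in 13.6(ii) with the rule of 9.1.1 and 13.5, and use the same text in all three sections. Apply it separately to IGFBP-2, HER2 and IGF-1R: detectable antigen-specific IgG with AI of at least 30% after vaccination, in a patient who did not meet that criterion at baseline.

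Report the baseline-positive proportion per antigen and arm, and state whether those patients stay in the denominator. Show their before and after values separately, or fix a rise rule before the sera are assayed. The sponsor would have to choose and justify any such threshold.

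Reconcile the sample used with both 13.9 (one month for response, six months for durability) and 5.7.2 (any post-vaccine sample).

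The cost is a wording amendment, with DCP and IRB approval under 14.3. No new samples or assays are needed: sera are already collected, and 10.2 has them analysed at the end of the study. Relative to a status-only reading, the reported rate may fall slightly because unchanged baseline antibody is excluded. Relative to literal 13.6, it may rise because high avidity is counted.
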